4.1 Data analysis general information

Unless otherwise specified: categorical data will be presented as frequencies (n) and percentages. Continuous data will be presented as n, mean, standard deviation (SD), median, minimum, and maximum.

4.1.1 General definitions

On-treatment assessment/event

The overall observation period will be divided into three mutually exclusive segments:

1. ***pre-treatment period***: from day of subject's informed consent to before date of first administration of study treatment
2. ***on-treatment period***: from date of first administration of study treatment to 98 days after date of last administration of study treatment (including start and stop date)
3. ***post-treatment period***: starting at day 98+1 after last administration of study treatment.

Note: If dates are incomplete in a way that clear assignment to pre-, on-, post-treatment period cannot be made, then the respective data will be assigned to the on-treatment period.

4.2 Analysis sets

For subjects whose actual treatment received does not match the randomized treatment, the treatment actually received will be used for the analysis, except for analyses using the Full analysis set.

The Per-protocol analysis set includes subjects compliant with the protocol and is characterized by the following criteria:

1. Subject received at least 9 months of the randomized treatment,
 - a. Within those 9 months, subject received at least 75% of the planned doses.
2. Subject does not have any major protocol violations (See [Table 4-1](#))

The Full analysis set includes all subjects to whom study treatment has been assigned by randomization. According to the intent-to-treat principle, subjects will be analyzed according to the treatment they have been assigned to during the randomization procedure.

The safety analysis set will include all subjects that received any study drug.

The PK (Pharmacokinetics) analysis set will include all subjects with at least one available valid (i.e. not flagged for exclusion) PK concentration measurement, who received any study drug and experienced no protocol deviations with relevant impact on PK data.

The PD (Pharmacodynamic) analysis set will include all subjects who received any study drug with at least a baseline or one post-baseline PD assessment.

The analysis sets and protocol deviation codes are related as follows:

Table 4-1 Protocol deviation codes and analysis sets

Category Deviation code	Text description of deviation	Data exclusion
Subjects are excluded from PP analysis set in case of these PDs:		
Inc04	Deviation from inclusion criterion 4-Evidence of one or more T1D autoantibody(ies): anti-GAD, protein tyrosine, anti-IA-2, anti-ZnT8 and anti-ICA.	Exclude subject from PP analysis set
Inc06	Deviation from Inc06-Peak stimulated C-peptide \geq 0.2 nmol/L after standard liquid MMTT when subject is metabolically stable, at least 2 weeks from diagnosis and within 56 days prior to randomization.	
Exc01	Any other diabetes present except auto immune type 1, by judgement of the investigator.	
Exc18	Ongoing, and up to 2 weeks prior to screening, use of medications that may affect glucose control (e.g., systemic steroids, thiazides, beta blockers).	
Subjects are excluded from PP and PK analysis set in case of these PDs:		
Exc20	Taking medications prohibited by the protocol	Exclude subject from PP and PK analysis sets
Subjects are excluded from PP analysis set in case of these PDs:		
OTH01	Subject potentially unblinded	Exclude subject from PP analysis sets
OTH02	Inv or Site Staff- Unblinded	Exclude only data after the date of unblinding
		Exclude only data after the date of unblinding

If updates to this table are needed, an amendment to the SAP needs to be implemented prior to DBL.

4.2.1 Withdrawal of Informed Consent

Any data collected in the clinical database after a subject withdraws informed consent from ALL further participation in the trial (meaning all criteria are checked on the eCRF), will not be included in the analysis. The date on which a subject withdraws full consent is recorded in the eCRF.

5 Statistical methods for Pharmacokinetic (PK) parameters

All subjects within the PK analysis set will be included in the PK data analysis.

5.1 Variables

Free CFZ533 concentration in plasma

For each PK sample, the actual recorded sampling time will be captured (CRF). The actual elapsed time since the first dose (with reference to the Dose Reference ID series #1; see Table 8-1 Blood sampling log in the Site Operations Manual) and since the specified dose (with reference to the Dose Reference ID series #2 in Table 8-1 in the SOM) will be calculated.

PK parameters

The following PK parameters will be determined and reported: C_{trough}, C_{trough,ss} (steady state) and C_{max} (.defined as concentration at the end of infusion 1.5 hr after start of infusion). They will be directly derived from the bioanalytical data in tables and listings.

Additional PK parameters (independent Novartis analysis) may be determined if data permit. A dose-independent, model-based analysis considering both IV and SC PK data may be performed as appropriate and will be reported in a separate, standalone modeling and simulation report. During modeling of PK data, the broad principles outlined in the FDA Guidance for Industry: Population Pharmacokinetics, will be followed.

5.2 Descriptive analyses

All statistical summaries and plots will be produced by body weight category: ≥ 30 to < 50 kg, ≥ 50 to ≤ 125 kg and overall.

CFZ533 plasma concentrations will be listed by treatment, subject, and visit/sampling time point. Descriptive summary statistics will be provided by treatment and visit/sampling time point,

Commercially Confidential Information

Pharmacokinetic parameters will be listed by treatment and subject and summarized by treatment and visit. Summary statistics will include mean (arithmetic and geometric), SD, CV (arithmetic and geometric), median, minimum and maximum.

Commercially Confidential Information

Arithmetic mean (SD) plasma concentration by time will be plotted on linear-linear and log-linear scale (all treatment groups in the same graph).

Overlaying individual plasma concentration by time profile will be plotted (one graph per treatment group, all subjects in the same graph) on linear-linear and log-linear scale.

Individual plasma concentration by time profile, by subject will be plotted on linear-linear and log-linear scale.

6 Statistical methods for Efficacy

All efficacy analyses will be performed on the full analysis set (FAS).

In case of dose adjustment occurring during the study, subjects will be analyzed under first doses received, censoring any observations post dose adjustment (if any) in statistical models and descriptive summaries.

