Study design	
CCFZ533X2207 is a Phase 2, non-confirmatory, investigator- and subject-blinded, randomized, placebo-controlled study to evaluate the safety, tolerability, pharmacokinetics, and efficacy of CFZ533 on preservation of residual pancreatic β-cell function in new onset T1DM in pediatric and young adult subjects.
 
The study is planned for 44 subjects randomized and assuming $\sim 18\%$ dropout rate, 36 subjects for primary efficacy (at 52 weeks) and safety endpoints (at 72 weeks).
 
Eligible subjects will be enrolled and randomized to active or placebo in a 2:1 ratio, stratified by age at first screening visit (≥ 18 to 21 years, followed by ≥ 12 to < 18 years).
 
The study timeline includes a screening period of approximately 8 weeks, a baseline period of 2 weeks, a treatment period of 52 weeks and a follow-up period following last dose of CFZ533 of 20 weeks.
 
This study will be the first study to evaluate CFZ533 in a pediatric population in any indication. Thus, enrollment will be staggered to evaluate safety and

	
tolerability on a rolling basis and enable gradual enrollment of younger age and lower weight groups.
 
The PK profile of CFZ533 will be evaluated throughout the study (Month 3, 6 and 9). Dosage adjustments may be introduced based on emerging PK data. The current assumptions considered allometric scaling based on body weight. The PK assumptions will be confirmed using population PK modelling.
 
Sequential enrollment by age and body weight (BW) categories include:
 
 • Cohort 1: age ≥ 15 to ≤ 21 years (older adolescents to young adults), body weight ≥ 40 kg to ≤ 125 kg. • Cohort 2: age ≥ 12 to ≤ 21 years (adolescents to young adults), body weight ≥ 30 kg to ≤ 125 kg. 
Before opening a subsequent cohort, safety and tolerability data from at least 6 subjects in Cohort 1 must be reviewed and deemed safe to proceed by the Sponsor and Lead Investigator.

Population	
The study population will be comprised of newly diagnosed T1DM pediatric and young adult subjects.
 
Forty-four subjects between the ages of 12 and 21 (inclusive) will be enrolled and randomized in the study in sequential order as outlined in the study design.

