4.2 Rationale for dose/regimen and duration of treatment

Overview of dose rationale: The CFZ533 dosing approach is in line with the allometric scaling assumptions and is predicted to ensure consistency of exposure and consequently comparable immunosuppression in a broad population of treated pediatric T1DM patients independent of body weight. Allometric scaling, based on a power law relationship between body weight and pharmacokinetic parameters, is widely used to predict pharmacokinetics of monoclonal antibodies; the emerging CFZ533 pharmacokinetic data from adult populations are in line with these allometric assumptions and body weight appears to be a good predictor of plasma pharmacokinetics of CFZ533.

The dosing regimen in this trial includes an initial intravenous loading dose to fully saturate the CD40 binding sites followed by a body weight adjusted subcutaneous maintenance dose CCI . The recommended body weight-adjustments aim to provide consistent plasma exposures for all treated young adult and pediatric subjects in this study (Figure 4-1).

While the maintenance subcutaneous doses are adjusted based on three predefined body weight categories, the initial intravenous loading dose (mg) is individualized based on the body weight of the individual subject. All subjects in the study will receive the weight based intravenous loading dose of 30 mg/kg. For example, the total intravenous loading dose for a hypothetical 70 kg subject will be 2100 mg (30 mg/kg x 70 kg) while a lighter subject with body weight of 30 kg will receive a lower total intravenous loading dose of 900 mg (30 mg/kg x 30 kg).

Dose rationale: The dosing rationale for CFZ533 in new onset T1DM subjects is based on exposure, safety and tolerability data from trials with CFZ533 in:

- Kidney transplant (kidney Tx; Study CCFZ533X2201-Part 2),
- Primary Sjögren's Syndrome (pSS; Study CCFZ533X2203),
- Graves' disease (GD; Study CCFZ533X2205),

- Myasthenia gravis (MG; Study CCFZ533X2204),
- Rheumatoid arthritis (RA) subjects (first in human Study CCFZ533X2101),

and based on efficacy data in kidney transplant, Primary Sjögren's Syndrome, and Graves' disease.

The CFZ533 dosing regimen includes,

- A body weight-adjusted intravenous (IV) loading dose of 30 mg/kg on Day 1 for all subjects in the trial, followed by
- A weight-tiered fixed subcutaneous (SC) dose administered weekly from Day 8 (Week 1) to CCI (last dose), which is based on the following body weight categories,

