6.1 Study treatment

Dosing of the study drug, CFZ533 (iscalimab) or placebo, will be based on body weight (details in [Section 4.2](#)).

Study drug dosage will be adjusted based on bodyweight recorded at Day 1 and then every 3 months during site visits ([Section 4.2](#)) to account for body weight gain or loss during the treatment period.

The first dose of study drug will be administered in clinic intravenously (IV) on study Day 1 and two subcutaneous (SC) dose will be administered under observation at a scheduled visit on Commercially Confidential Information Thereafter, weekly subcutaneous (SC) doses may be administered at home or at Investigator site (see Assessment Schedule [Table 8-1](#)).

Every effort should be made to respect the weekly dosing schedule regardless of whether dosing is planned in clinic, off-site, or at home by subject or guardian in order to maintain target plasma CFZ533 exposure levels, and ensure complete CD40-CD154 pathway blockade in target tissues, and permit assessment of drug safety and potential efficacy. A \pm 3 days window may be applied to the study drug SC administrations (regardless of whether dosing is planned in clinic, off-site, or at home by subject or guardian). In all cases the original visit and dosing schedule should be maintained, so that the visits and doses must continue to be administered as per the original schedule, and the administration schedule should not be recalculated from the time of the last dosing. For example, if the subject's usual dosing day is Wednesday, but a visit is planned for Friday, the dose would be administered at the time of the Friday visit (on-site or off-site), but the next dose administration would continue on the following Wednesdays as originally planned.

One delayed dose or missed dose: Every effort should be made to administer the study drug dose within the \pm 3 days intended window. However, in case of exceptional medical or operational need, or unintentional omission (*i.e.* forgotten dose) study drug administration may be delayed by a maximum of 6 days before it is considered a missed dose (*i.e.* if subject's dosing day is Wednesday the late dose may be administered up to and including Tuesday, but a dose is considered missed on the day the next scheduled dose is due).

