6.1.3 Statistical model, assumptions and hypotheses

The primary statistical analysis will be done using the Full analysis set (treatment policy estimand). As a secondary analysis, the model will be run using the Per Protocol set (hypothetical strategy estimand). For both analyses, all data collected for subjects in the respective analysis sets will be used in the model (e.g. including data after study drug discontinuation). Stimulated C-peptide AUC by the standard MMTT, normalized by the duration of measurements, will be analyzed with a mixed model repeated measures (MMRM) analysis. The natural log of the AUC (Weeks 12, 24, 36 and 52 on treatment) will be the dependent variable in this analysis. Independent variables will include age group (≥ 12 to < 18 , ≥ 18 to 21) treatment, visit, and the treatment by visit interaction.

The natural log of the baseline AUC will be used as a covariate and subject will be used as a random effect. Back transformation (exponential) will be used to obtain the least square geometric mean of each treatment, the ratio of CFZ533 to placebo, the 80% confidence interval of the ratio, and the one-sided p-value of treatment benefit for each time point. The model-based estimated fixed effects and p-values will be presented, along with the overall treatment effect.

Note 1: Any C-peptide AUC collected at a post-baseline unscheduled visit will be assigned to the closest scheduled visit for the model-based analysis; in the case of a tie it will be assigned to the previous visit (e.g. unscheduled collected at Week 30 will be assigned to Visit 24 for the model-based analysis). If a C-peptide AUC is already available at the scheduled visit, the average of the scheduled and unscheduled visit AUC will be used in the model.

Note 2: Week 52 C-peptide AUC which was not actually collected 365 +15 days after the first dose (i.e. due to it being the EOT assessment for early treatment discontinuation) will not be used for the model-based analysis as a Week 52 assessment, but will be assigned to the closest visit.

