6.2.2 Descriptive analyses

- For stimulated C-peptide AUC by MMTT at Week 72, total daily dose of insulin, insulin-dose adjusted HbA1c, their change and percent from baseline will be summarized by descriptive statistics for each treatment group and each time point (where applicable).

- The proportion of subjects with remission and each of the three components (full remission and two different criteria for partial remission) and subjects with detectable C-peptide will be descriptively summarized for each treatment group and each time point and overall study period.
- Time to undetectable C peptide will be analyzed by Kaplan-Meier methods by treatment group. Estimates of median time to undetectable C peptide and proportion of subjects with detectable C-peptide and their confidence intervals for each treatment group and each time point (where applicable) will be produced. Time to Peak C-peptide \leq 0.2 pmol/mL (or below LLOQ) and proportion of subjects with C-peptide \geq 0.2 pmol/mL will be analyzed similarly.

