6.2.3 Statistical model, assumptions and hypotheses

Normalized stimulated C-peptide AUC by MMTT at Week 72 will be analyzed in the same manner (and using the same model) as the primary objective. C-peptide AUC at all time points up to and including Week 72 will be included. The baseline by visit interaction term may also be considered for this model.

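### The SAP censors efficacy data after a dose adjustment, yet defines the primary analysis as treatment policy on all collected data, without ranking the two rules or defining the trigger

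*SAP*

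**What the plan says.** The opening text of SAP 6, which covers all efficacy analyses on the full analysis set (FAS), says that in case of dose adjustment "subjects will be analyzed under first doses received, censoring any observations post dose adjustment (if any) in statistical models and descriptive summaries". It makes no exception for the primary model.

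SAP 6.1.3 says: "The primary statistical analysis will be done using the Full analysis set (treatment policy estimand"). It adds that, for this analysis and for the per-protocol (hypothetical strategy) analysis alike, "all data collected for subjects in the respective analysis sets will be used in the model (e.g. including data after study drug discontinuation"). SAP 6.1.3.1 repeats FAS, no imputation and missing at random, and does not mention censoring.

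Under SAP 6.2.3, C-peptide AUC at Week 72 "will be analyzed in the same manner (and using the same model) as the primary objective". Remission at Week 52 is handled by description only (SAP 6.2.2): "The proportion of subjects with remission and each of the three components (full remission and two different criteria for partial remission") is summarised by arm.

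The protocol uses the language of adjustment for two different things:

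- The study design entry of the protocol summary says: "Dosage adjustments may be introduced based on emerging PK data".
- Protocol 6.1 says: "Study drug dosage will be adjusted based on bodyweight recorded at Day 1 and then every 3 months during site visits".

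Protocol 4.2 presents the weight tiers as part of the regimen itself: "A weight-tiered fixed subcutaneous (SC) dose administered weekly from Day 8 (Week 1"). The tier boundary is 50 kg, and eligible weights run from 30 to 125 kg.

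**The concern.** For a subject whose dose is adjusted, one rule removes later C-peptide values and the other keeps them. Only the second fits a treatment-policy estimand. Two programmers, each following a sentence of the SAP, would produce different primary datasets. If the question is settled after unblinding, the choice of primary dataset can depend on the data.

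The combined effect is also odd. A subject who stops the drug keeps all later values, while a subject who stays on drug at a changed dose loses them. If tier changes count as adjustments, this would apply to someone following the assigned regimen exactly who crosses 50 kg. That subject would lose every MMTT value after the change, including Weeks 52 and 72.

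The remission endpoint is more exposed than the primary one. It is a descriptive proportion, so the censoring rule applies directly. The all-data sentence in SAP 6.1.3 concerns the model only, and no model recovers a censored Week 52 status.

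**Working it through.** **The rules side by side, for a subject with a dose change before Week 52**

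| | SAP 6 | SAP 6.1.3 |
|---|---|---|
| C-peptide before the change | kept | kept |
| C-peptide after the change, still on drug | censored | kept |
| C-peptide after stopping drug | not addressed | kept |
| Declared estimand | none stated | treatment policy (FAS); hypothetical (per protocol) |
| Definition of dose adjustment | none visible | not mentioned |

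The second row cannot be satisfied both ways.

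**The plan's own power figure.** Protocol 12.8.1 gives 36 evaluable subjects at 2:1 (24 and 12), one-sided alpha 0.1, a ratio of 1.375 and a CV of 70%.

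- SD of log AUC = sqrt(ln(1 + 0.7²)) = sqrt(0.3988) = 0.6315.
- Standard error = 0.6315 × sqrt(1/24 + 1/12) = 0.2233.
- Non-centrality = ln(1.375)/0.2233 = 0.3185/0.2233 = 1.426, with 34 df.
- Power (non-central t) = 55.1%, against 55% stated. At ratio 1.56 it is 75.4%, against 75% stated. The sample-size figures are sound.

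**Effect of censoring.** The documents give no rate of dose change, so three inputs are assumptions:

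- f, the share of each arm censored before Week 52: 5% to 20% (about 2 to 7 of 36).
- r, the between-visit correlation: 0.5 to 0.8, the same for every pair of visits (as the subject random effect implies).
- k, the earlier on-treatment MMTT visits kept: 1 to 3. The first weight recheck after Day 1 is Week 12 (Protocol 4.2), which is also an MMTT visit (Protocol 8.2.1), so at least one is normally kept.

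Formulas: R² = k r² / (1 + (k − 1) r). Variance of an arm's Week 52 mean = 0.3988 × [(1 − R²)/(n(1 − f)) + R²/n]. Degrees of freedom = 36(1 − f) − 2.

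Worst corner (k = 1, r = 0.5, f = 0.20):

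- R² = 0.25.
- Placebo variance = 0.3988 × [0.75/9.6 + 0.25/12] = 0.0395. The active arm has half of that, 0.0197.
- Standard error = sqrt(0.0592) = 0.2433, which is 1.090 times the uncensored value.
- Non-centrality = 0.3185/0.2433 = 1.309, with 26.8 df. Power = 50.3%.

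| Share censored | Power, k = 1, r = 0.5 | Power, k = 3, r = 0.8 |
|---|---|---|
| 0% | 55.1% | 55.1% |
| 5% | 54.0% | 54.7% |
| 10% | 52.8% | 54.2% |
| 15% | 51.6% | 53.7% |
| 20% | 50.3% | 53.2% |

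The other combinations of k and r lie between these columns. The loss is 0.4 to 4.8 points, and the Week 52 standard error is 0.7% to 9.0% larger.

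**The case against.** - **The trigger probably means PK-driven changes only.** SAP 6 is worded conditionally, whereas weight rechecks are certain and scheduled. The protocol summary uses nearly the same term for PK-driven changes, and Protocol 4.2 makes the weight tiers part of the regimen. This is the more natural reading, so the 50 kg scenario is a possible consequence and not an established one. It narrows the trigger without removing the conflict: a PK-driven change would still be censored under SAP 6 and kept under SAP 6.1.3.
- **Withheld text may define the trigger.** Protocol 4.4 and 12.7, part of Protocol 6.5, and SAP 2 and 3 are not visible. This stands as a limit on the trigger point. The two conflicting sentences are themselves fully visible.
- **The rules could address different events.** An estimand may treat discontinuation by treatment policy and a dose change by a hypothetical strategy. SAP 6.1.3 does not say that. It uses all collected data and names discontinuation only as an example, while SAP 6 names statistical models without exception.
- **The effect is small and rests on assumptions.** This is correct. The starting 55.1% also comes from an unadjusted two-sample calculation, whereas the planned model adjusts for baseline, so these are not the power values of the planned MMRM.
- **First-dose data only could be a legitimate choice in a non-confirmatory Phase 2 study.** It could, but it would then need a different estimand label from the one in the SAP.

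**Conclusion.** The concern holds. SAP 6 and SAP 6.1.3 give incompatible inclusion rules for any subject with a dose adjustment, and applying SAP 6 would not estimate the declared treatment-policy estimand. The Week 72 model and the per-protocol analysis inherit the problem. For the Week 52 remission proportions, only the censoring rule applies.

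Confidence is high on the conflict itself. It is lower on what counts as an adjustment, because of the withheld text. The practical effect runs from nil (PK-driven changes only, none occurring) to a loss of a few points of power under the assumed shares, correlations and visits kept. Affected subjects still contribute their earlier visits to the MMRM. This should be fixed because the primary dataset must be unambiguous, not because of the power loss.

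**What to change.** Before database lock, amend SAP 6 and 6.1.3 to say:

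1. The treatment-policy primary analysis and the Week 72 analysis do not censor after a dose change. All observations are analysed under the randomised arm, as SAP 4.2 already provides for the FAS.
2. For analysis purposes, body-weight tier changes are part of the assigned regimen and never trigger censoring.
3. If censoring after a PK-driven regimen change is wanted, it is a labelled supplementary analysis with a defined trigger. State whether it also applies to the per-protocol hypothetical-strategy analysis.
4. Say explicitly how the Week 52 remission summaries treat subjects with a dose change, consistent with items 1 and 2.

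The cost is a short SAP amendment (a rule, a definition and a cross-reference) and no new data. The downside is that, after a PK-driven change, the primary estimate reflects the regimen as given and not the original dose alone. This is an analysis rule and takes no position on dosing.

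It does not settle a separate discrepancy: Protocol 12.4.3 excludes data after drug discontinuation from the primary efficacy analysis, and SAP 6.1.3 keeps them. That needs its own reconciliation.
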